Recently, a focus on care coordination (e.g. care planning, navigating healthcare system) has emerged in the literature for those with chronic disease [6]. At the same time, science has emerged demonstrating how patient education programs that promote self-management for those with specific chronic conditions have positive effects on health behaviours, improved health status, and decreased health care costs [7]. Health coaching research to date has, for the most part, focussed on improving motivation and adherence to health behaviours and to support lifestyle change in order to prevent the negative course of a disease [8]. Health coaching is tailored to the patients' knowledge needs, and can be delivered through many means – one to one or via telephone or technology [9].

The preschool years are a time of stress for families as their preschool child awaits assessment, or even as they receive services for brain-based disorders. Similarly, the system and society struggle to meet needs of families in a timely and appropriate manner in the face of escalating costs. Given these struggles, there is need to examine whether a health-coach style of intervention coupled with parent education delivered through an online platform can be effective in empowering families, by delivering information, providing social (parent to parent) supports, and decreasing demand on health and developmental services. This innovation provides a significant service re-design in a system at critical point of transition.

AIMS AND HYPOTHESES

Primary Hypotheses:

- (1) A standardized approach to “developmental coaching” (i.e. coach + online education tools + peer support network) is *feasible* in the real-life context and *acceptable* to mothers and fathers and can be delivered across multiple inter-provincial sites that recruit patients from urban/suburban/rural settings.
- (2) A standardized approach to “developmental coaching” enhances *parental health* (parents' empowerment and sense of competence, quality of life, and minimizes parenting stress), *family health care experience* (care coordination experience and process of care) at similar *health care cost* (economic analysis), when compared to usual care.

Secondary Hypotheses:

- (3) Given the differences that exist in caregiver burden, Fathers will contact the coach and use the online platform less frequently than mothers. (*sex/gender hypothesis*)

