Once past the feasibility stage, outcomes will be measured at 8 months and 12 months after recruitment. The primary outcome of interest in the RCT is the *parents' ability to self-manage and promote their child's development*. Thus, the primary outcome measure is the Family Empowerment Scale, which focuses on empowerment at the family (managing the day to day), services (working with system to receive adequate services) and community (finding or advocating for needed supports, policies, agencies) levels [13]. Its psychometric properties are acceptable. A second measure will be the Parents' Sense of Competence Scale which measures satisfaction (anxiety, motivation, frustration) and efficacy (capability, problem-solving) with parental roles [14].

Secondary measures of intervention efficacy apply the Triple Aim Framework and will include:

1. Parental well-being: SF-36 [15] (quality of life) and the Parenting Stress Index [12] (parent stress level).
2. Family health care experience: Measure of Process of Care [16] (the extent to which care is family-centred)

3. Health care costs/ service utilization patterns: the Resource Utilization Questionnaire (adapted from Drs. [name] and [name]) uses standardized metrics for the evaluation of costs (health care and out-of-pocket), consequences and benefits from the patient, provider and health system perspectives.
4. Care and social networks: Care and social networks will be tracked using Igloo analytics. This will include tracking during the transition from preschool to school-aged services and the identification of professional and community supports.
5. Engagement of mothers and fathers with BRIGHT program: Analysis of electronic contact data from Igloo platform by mothers and fathers (gender).

Exploratory measures will include:

Child's functional abilities and independence: Vineland – daily living skills, socialization, etc .. Importantly, in the spring of 2017, an online “needs assessment” survey was conducted with Canadian families to influence the content of the coach intervention and to determine the outcomes of greatest interest to families and administrators.

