Descriptive statistics will be used to characterize our sample in the experimental and control arms. The primary analysis is to ascertain benefit of the BRIGHT system (Coach + online education tools + online peer support) compared to usual care (control) will be between group (intervention vs control) comparison of primary and secondary outcomes using t tests (two-sided, $p<.05$). Statistical comparisons will be made at 8- and 12- months post enrolment, to determine if group differences manifest early and if they continue to improve or stabilize. This will be important in determining whether the BRIGHT system is necessary over a prolonged period (8 vs 12 months) to achieve its goals. Principles of intent-to-treat analysis will be applied. Repeated measures with mixed model analysis will be used to assess effect of group category and province with intervention at two time points. Within the intervention group, predictors of change scores between baseline and outcomes (dependent variable) will be tested to determine which children/families are more likely to be responsive to the BRIGHT system. Multivariate linear regressions will be conducted with independent variables, to include: parent readiness score, sociodemographic factors, child's functioning (Vineland), province, and engagement in the Igloo platform. The structural properties of the network (Igloo) will be analysed using UCINET [17]. Network analysis related to patterns of use of the online platform will be correlated with the outcome measures of interest in this study.

Sample size:

We will recruit 392 participants; we project a sample size of 352 based on: i) two-sided test of the null hypothesis at $\alpha=.05$, ii) $\beta=.80$, iii) 10% attrition; iv) difference of 0.3 SD.

Studies as of yet have not identified a minimal clinically important difference (MCID) for our primary outcome measure (the Family Empowerment Scale) that could be used to estimate sample size calculation. In the absence of a “clinimetric” MCID, a distribution-based methods approach is commonly applied that proposes a fraction of the pooled Standard Deviation (i.e. utilize effect size estimates). In this case, the difference of 0.3 standard deviation can be used to detect modest effects that may be clinically significant; or 0.5 SD for moderate to large effects [18, 19].

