IMPLICATIONS FOR CHILD AND FAMILY WELL BEING - PRACTICE AND POLICY

The preschool years between 3 and 6 years of age are a time of great developmental change and a time of great concern for parents who see differences in their child’s development. Coordination of services, for those children receiving them can be challenging and confusing. Waiting for services for those not yet

receiving them can lead to frustration and fear. From a policy and health/social system administrator perspective, despite large investments, waiting lists often exist.

At the conclusion of this study, should the hypotheses be proven to be correct, the following impact will be seen for the following groups:

- *Families:* This study will produce an evidence-based mechanism to support families during times of uncertainty. It will be effective across developmental severity levels making it very generalizable. It will enable families in feeling supported, will enhance family empowerment, will support enhanced family well-being. With guidance regarding services, it is expected that there will be reduced travel time and time off work for families, thereby reducing costs to families.
- *Policy makers and health administrators:* The results and KT products will provide mechanisms to facilitate discussion regarding how the program is delivered regionally. It is anticipated that the program and its key ingredients could be delivered through multiple means, allowing governments to tailor its use to reflect their provincial, regional and local nuances.
- *Service Delivery/Developmental Programs:* The draw on services across provinces will be reduced as families receive information that prevents them from being in the incorrect queue for services and assists them in coordinating their own services as has been done with other self-management programs in adults with chronic disease. Rural and remote service delivery will be enhanced through this care, which can be delivered from a distance.

TABLE 1. MILESTONES, DELIVERABLES

Major Project Activities/ Milestones	Year 1 (M)ilestones	Year 2 (M)ilestones	Year 3 (M)ilestones/ (D)eliverable	Year 4 (M)ilestones/ (D)eliverable	Year 5 (M)ilestones/ (D)eliverable
Clinical study protocol and ethics review	(D) Protocol finalized with family input (D) Ethics approves finalized protocol across sites				

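### Quality of life, parenting stress and process of care are primary by hypothesis, secondary by outcome list and part of the primary analysis, and no rule says when Hypothesis 2 is supported

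*Protocol*

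**What the plan says.** The protocol sets the tier of these measures in three places.

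- **Aims and Hypotheses.** Under "Primary Hypotheses", item (2) predicts that coaching improves parental health and family health care experience at similar cost. Parental health covers empowerment, "sense of competence, quality of life, and minimizes parenting stress". Family health care experience is spelled out as "care coordination experience and process of care".
- **Baseline, ongoing and final data collection and outcome measures.** "Thus, the primary outcome measure is the Family Empowerment Scale", and the Parents' Sense of Competence Scale is introduced as a second measure. The next list opens "Secondary measures of intervention efficacy apply the Triple Aim Framework and will include". It contains the SF-36, the Parenting Stress Index, the Measure of Process of Care and the cost questionnaire. Only the Vineland is labelled exploratory. Table 2 agrees that the SF-36, stress and process-of-care measures are secondary, and puts the competence scale under its primary heading.
- **Statistical analyses.** The primary analysis is the "between group (intervention vs control) comparison of primary and secondary outcomes using t tests", two-sided at p<.05, with comparisons at 8 and at 12 months.

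The sample size section assumes one two-sided test at .05, 80% power (printed as a beta of .80) and a 0.3 SD difference. It gives 352 analysed and 392 recruited. It again calls the Family Empowerment Scale the primary outcome measure.

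**The concern.** The same three measures belong to a primary hypothesis, to the secondary outcome list and to the primary analysis. No analysis plan can follow all three statements; it would have to override at least one. So this is a conflict in the protocol's own text, not a detail left for later.

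The protocol also does not say whether Hypothesis 2 is supported when any component succeeds or only when all do. If empowerment showed nothing and stress reached p<.05 at 8 months, one analyst could report partial support for a primary hypothesis and another could report failure. The first reading carries an uncontrolled error rate. The second carries a power that was never calculated. These are alternatives, and only one can apply.

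**Working it through.** **1. The plan's own sample size.** Inputs from the sample size section: two-sided alpha .05 (z = 1.960), power .80 (z = 0.842), difference 0.3 SD.

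- n per arm = 2 × (1.960 + 0.842)² / 0.3² = 174.4, so 175 per arm and 350 in total. The stated 352 (176 per arm) gives power of 80.4%.
- Recruitment: 352 / 0.90 = 391.1, or 392 as an even total. This matches.

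The stated size is therefore right for one test of one measure at one visit.

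**2. The three statements side by side.**

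| Component | Aims and Hypotheses | Outcome section and Table 2 | Statistical analyses |
|---|---|---|---|
| Quality of life (SF-36) | primary hypothesis | secondary | in the primary analysis |
| Parenting stress (Parenting Stress Index) | primary hypothesis | secondary | in the primary analysis |
| Process of care (Measure of Process of Care) | primary hypothesis | secondary | in the primary analysis |

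**3. If any one component could support Hypothesis 2.** Only results favouring BRIGHT could support it, so the nominal rate per test is .05 / 2 = 2.5%. Assumptions: no true effect, and one score per measure (subscales would raise the rates). The protocol gives no correlations, so I take 0 to 0.7 between outcomes and 0.5 to 0.7 between visits.

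- One visit, 3 tests: with independence, 1 − 0.975³ = 7.3%. Simulation (400,000 multivariate normal draws, critical value 1.96) gives 6.2% at correlation 0.5 and 5.5% at 0.7.
- Two visits, 6 tests: simulation gives about 11% at 0.5 between outcomes and 0.5 between visits. The range is 8.9% (0.7 and 0.7) to 13.0% (0 and 0.5).

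**4. If all components must succeed.** Take five scales (empowerment, competence, SF-36, stress, process of care) at one visit, each with a true 0.3 SD effect and 80% power.

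- Independent: 0.80⁵ = 32.8%.
- Correlation 0.5: 51%. Correlation 0.7: 59%.

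This leaves out care coordination and similar cost, which are also in Hypothesis 2 and could only lower the figure. The protocol argues for 0.3 SD on the Family Empowerment Scale only; applying it to the other scales is my assumption.

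**The case against.** The strongest reply is that the outcome tiers are clear. The outcome section names the Family Empowerment Scale as primary, the sample size section repeats it, and Table 2 agrees that the three disputed measures are secondary. The analysis sentence itself keeps the words primary and secondary apart. On this reading, the primary analysis only means the main between-group comparison, as distinct from the predictor regressions and network analysis that follow. Multiplicity rules for secondary outcomes are also commonly left to an analysis plan, which is not at hand.

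Much of this stands. The lack of a testing order among secondary outcomes is not a finding here, and the named primary measure shows which way to reconcile the text. But the reply does not remove the three measures from a primary hypothesis, and it needs a charitable reading of the analysis sentence.

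Three stronger readings are tempting and are not supported:

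- **A chance secondary result would be enough for Hypothesis 2.** The protocol states no such rule. The hypothesis is worded as a conjunction, ending with similar cost, so a single result on stress would not satisfy it as written.
- **The relevant error rate is the two-sided one**, about 22% over two visits. Half of those results would favour usual care and could not support the hypothesis.
- **The impact section licenses a well-being claim when empowerment is null.** It does say the study "will enhance family empowerment, will support enhanced family well-being", but conditionally on the hypotheses (plural) proving correct, and it sets no decision rule.

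**Conclusion.** The point holds as a contradiction in stated text together with a missing rule for Hypothesis 2. It does not show that the trial will make a false claim.

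Its size depends on the reading. Under an any-component reading, the favourable false-positive rate on the three measures is about 11% over two visits (9% to 13%) or about 6% at one visit (5% to 7%), against 2.5%. Part of the two-visit figure arises because no primary visit is named; the one-visit figure shows what remains once a visit is fixed. Under an all-components reading, joint power is about 51% (33% to 59%) in place of 80%, before care coordination and cost are counted. All these figures rest on the assumed correlations and one score per measure, and the power figures also on an equal 0.3 SD effect on every scale. The correction is worth making because it is cheap and settles the conflict before results are known.

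**What to change.** - **Statistical analyses.** Limit the primary analysis to the Family Empowerment Scale. List the t tests of secondary outcomes as secondary analyses, reported as estimates with 95% confidence intervals and supportive only. Keep the 8- versus 12-month comparison as a secondary question.
- **Aims and Hypotheses.** Move quality of life, parenting stress, health care experience (care coordination and process of care) and cost to secondary hypotheses, to match the outcome section.
- **Parents' Sense of Competence Scale.** Give it one stated tier. Hypothesis 2 includes it, the outcome section calls it a second measure, Table 2 puts it under primary, and the mixed model in the sample size section targets both empowerment and competency. Align all four. If it stays primary, state how alpha is shared with the Family Empowerment Scale or in what order the two are tested.

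Other choices, such as formal gatekeeping of the secondary outcomes, are optional and not needed to remove the contradiction.

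The cost is wording only, with no extra families or data, and 352 analysed and 392 recruited stand for a single primary test. Sharing alpha with the competence scale would need the size rechecked. The small downside is that an isolated p<.05 on a secondary measure can no longer be presented as confirming a primary hypothesis.

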We aim to recruit a sample of 350 participants (randomized to either intervention or control group) across the four sites. This will be approximately 100 from British Columbia, 100 from Quebec, 75 from Manitoba and 75 from Nova Scotia. In order to be able to detect modest effects that may be clinically important (0.3 SD), this would require recruitment of a sample of 392, accounting for 10% attrition, for a sample of 352. Furthermore, this larger sample size would enable us to account for cluster randomization. We expect that all participants are independent, whether or not they live in any of the provinces. Nonetheless, it is conceivable that the association within provinces is slightly stronger (weak ICC=0.100) than the association between participants across provinces, due to environmental context (i.e. different health care and social service systems). A sample size of 346 (recruit 384, 10% attrition) would allow us to account for cluster randomization. We will apply a linear mixed model to account for the possible effect of province on the benefits of treatment on empowerment and parent competency.

PLANS FOR KNOWLEDGE TRANSLATION

The results of this study will be relevant to families, health service administrators, policy makers and providers.

Families: Families will be important consumers of the results of this study. In order to determine how best to communicate the results to them, a focus group of families will be brought together. They will guide strategy and tactics with respect to the study results. The content for this knowledge translation will be particularly focussed on the benefits and challenges from the perspective of families. With respect to tactics, it is anticipated that family councils, childhood-disability focussed organizations, the media, family-guided web-based materials and providers will be modalities undertaken to reach families. This plan will be modified subsequent to the focus group with families after the conclusion of the study.

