Anticipated Outcomes:	
 • Parents will be more empowered and knowledgeable, and make more informed decisions about their child's care and development • Services accessed will be appropriate based on the child's and family's needs and developmental services will be more cost-effective • Providers will feel confident that their clients are receiving appropriate services and supports based on client needs
Anticipated Impacts:	
A more responsive health care system that meets the developmental needs of children and the health and knowledge needs of parents.
 
The electronic platform (Igloo) will be tested with respect to its utility as an information and support network, for consideration for other chronic diseases of childhood.

	Research trainees will be well prepared to pursue future child health research with a strong inclusion of families and their support networks.
--	--

TABLE 2. SUMMARY OF MAIN PREDICTOR AND OUTCOME MEASURES

VARIABLES	MEASURE
PRIMARY PREDICTOR	
Intervention versus control group	Randomization to one group
Other Key Variables	
Child's age	Age at recruitment in months to one decimal place
Child's sex	Male/female
Parental involvement in the intervention	Mother vs father; # of uses of Igloo platform (areas: coach, online education tools, peer support)
Socioeconomic factors	Parents' education level, postal code
Readiness for health coach model	Readiness for coaching questionnaire (3-points)

OUTCOMES	
PRIMARY	
Empowerment (ability to manage and take charge) at the family, services and community levels	Family Empowerment Scale
Parental satisfaction and efficacy with competency	Parents Sense of Competence Scale
SECONDARY	
Family stress level	Parenting Stress Index
Parental well-being (quality of life)	SF-36
Family-centered care provided by coach to include educational benefits	Measure of Process of Care

Health service utilization and costs	Resource Utilization Questionnaire (adapted from [name] and [name])
Profile Form	Surveys on background of participant & family structure
Demographic Form	Survey on family socioeconomic status and education level
Child's functional abilities	Vineland
Survey on parent/caregiver mental health	Parenting Morale Index

REFERENCES

1. Majnemer, A., et al., *A new look at outcomes of infants with congenital heart disease*. Pediatric neurology, 2009. **40**(3): p. 197-204.

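### No single primary test is fixed: Table 2 has two primary measures where the text names one, neither 8 nor 12 months is the deciding visit, and the 8-versus-12-month duration sentence claims more than two arms can show

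*Protocol*

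**What the plan says.** **Primary measure.** In the section on data collection and outcome measures the wording is singular: "Thus, the primary outcome measure is the Family Empowerment Scale". The Parents' Sense of Competence Scale follows as a further measure, ahead of the list of secondary measures and not part of it. The Sample size section again treats FES alone as primary when it discusses the minimal important difference. Table 2, however, has two rows under its primary heading: empowerment (FES) and "Parental satisfaction and efficacy with competency" (the competence scale). The last sentence of the Sample size section applies the mixed model to "the benefits of treatment on empowerment and parent competency". Primary Hypothesis 2 groups "empowerment and sense of competence, quality of life, and minimizes parenting stress" under parental health.

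**Primary visit.** Under Statistical analyses, the primary analysis is a between-group t test of primary and secondary outcomes, two-sided at p<.05, and "Statistical comparisons will be made at 8- and 12- months post enrolment". Neither visit is named as deciding. A further analysis is planned: "Repeated measures with mixed model analysis will be used to assess effect of group category and province with intervention at two time points". It is not said to replace the t tests or to supply the one deciding test.

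**Duration.** Of the two sets of comparisons the same section says: "This will be important in determining whether the BRIGHT system is necessary over a prolonged period (8 vs 12 months) to achieve its goals". The Trial design section describes two arms, and the Study procedures section sets 12 months of coach contact for the intervention arm.

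**The concern.** A trial sized on one test at .05 needs one identifiable primary test. Here there are two candidates if FES alone is primary (FES at 8 and at 12 months), and four if Table 2 governs. With no deciding measure or visit, benefit could be claimed on whichever came out significant, at an error rate above the .05 behind the sample size. A rule requiring significance at both visits would not inflate the error, but the protocol does not state one.

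The duration sentence is a separate and smaller matter. Every intervention family is planned to be coached for 12 months, so what happens when coaching stops at 8 months is never observed. Two separate t tests do not test change between visits either: significance at one visit and not at the other can arise by chance when the true effect is the same at both. Since the protocol plans a policy dialogue on implementation, a mistaken conclusion about programme length could reach practice.

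**Working it through.** **Inputs.** From the protocol: two-sided alpha .05, power 80% (written as beta = .80 and read as power), difference 0.3 SD, attrition 10%, 1:1 allocation, visits at 8 and 12 months. The protocol gives no correlation between visits or between measures, so a range is assumed.

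**1. The protocol's own figure.** The normal approximation gives 2 × ((1.960 + 0.842)/0.3)² = 174.4, so 175 per arm. The t-test version gives 175.4, so 176 per arm and 352 in total. Recruitment is 352/0.9 = 391.1, so 392. The stated 352 and 392 are reproduced exactly, as a design for **one** test at .05.

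**2. False-positive chance, FES at two visits, either one counting.** This is 1 − P(|Z₁| < 1.96 and |Z₂| < 1.96) under a bivariate normal with correlation r. For r = 0 it is 1 − 0.95² = 9.75%.

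| r between visits | 0 | .5 | .6 | .7 | .8 | .9 |
|---|---|---|---|---|---|---|
| At least one p<.05 | 9.75% | 9.1% | 8.75% | 8.35% | 7.8% | 7.0% |

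**3. The same for the four tests under Table 2.** The correlation between any two statistics is the product of the between-visit and between-measure correlations; results are by simulation. For independent tests it is 1 − 0.95⁴ = 18.5%.

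| Between visits / between measures | 0/0 | .5/.3 | .7/.4 | .8/.6 | .8/.7 | .9/.8 |
|---|---|---|---|---|---|---|
| At least one p<.05 | 18.5% | 16.9% | 15.3% | 13.4% | 12.8% | 10.8% |

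If all four statistics share one correlation, the chance is 15.6% (.5), 13.1% (.7), 11.4% (.8) and 9.4% (.9).

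**4. Chance disagreement between visits.** Suppose the true effect is 0.3 SD at both visits. Each statistic then has mean 0.3 × √(n/4). The chance that exactly one test is significant is 2 × [P(one given test not significant) − P(both not significant)].

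| Evaluable n | Mean | Power per test | r=.5 | r=.6 | r=.7 | r=.8 |
|---|---|---|---|---|---|---|
| 352 | 2.81 | 80% | 22.3% | 19.9% | 17.2% | 14.0% |
| 315 | 2.66 | 76% | 25.4% | 22.6% | 19.5% | 15.9% |

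The second row uses the 350 also given as the recruitment aim: 350 × 0.9 = 315.

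**5. What the data can say about change between visits.** The 95% CI half-width of the treatment-by-visit contrast at 352 is 1.96 × √(2(1 − r) × 4/352). That is 0.21 SD at r = .5 and 0.13 SD at r = .8.

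**6. Price of keeping both visits primary.** At .025 each, 2 × ((2.241 + 0.842)/0.3)² = 211.2, so 212 per arm and 424 evaluable; 424/0.9 = 471.1, so 472 recruited. With 352 evaluable, power at .025 is 71.7%.

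**The case against.** **The text may intend two primary measures.** The competence scale stands in the primary-outcome paragraph and is missing from the secondary list, which fits Table 2. This is a fair reading. But the wording is singular in two places, and if two primary measures were meant, the one-test sample size does not cover them. Either reading calls for a correction.

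**Primary Hypothesis 2 and the mixed-model sentence are weak support.** The hypothesis also covers quality of life, stress, care experience and cost, and its quality-of-life and stress measures are secondary elsewhere. This stands: being in the hypothesis does not make a measure primary. The contradiction rests on the text against Table 2.

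**The percentages answer a rule the protocol does not state.** This also stands, and they are given only on that condition. The ends of the ranges are not equally plausible: independence is unlikely for the same parents four months apart, and at a between-visit correlation of .9 the FES figure falls to 7.0%, still above 5%.

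**A SAP may settle details.** It may set a testing order or an alpha split, so their absence is not the complaint. A protocol that defines its primary analysis should still name the measure consistently and name the visit.

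**The duration wording is soft, a mixed model is planned, and nothing says that discordant t tests will be read as change.** This is true and makes the point minor. Yet the text does not tie the early-versus-late question to that model, and no analysis can supply the missing 8-month stopping arm.

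**424 is an upper bound.** It comes from an equal split that ignores correlation. Exact control at a correlation of .8 (about .031 per test) would need about 400 evaluable, still more than 352.

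**Conclusion.** The concern holds. The protocol disagrees with itself on whether there is one primary measure or two, and it defines a primary analysis at two visits without saying which decides, while its sample size is that of a single test at .05. If any significant primary result counted, the false-positive chance would be about 8-10% on FES alone (between-visit correlation .8 down to 0) and about 11-19% under Table 2 (.9 between visits and .8 between measures, down to independence). The correlations are assumed, and there would be no inflation if both visits had to be significant. This must be fixed before any data by arm are analysed.

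The duration sentence is a lesser fault of wording. The design can describe the effect at 8 and at 12 months under continued coaching, but not whether 8 months would be enough. With an identical 0.3 SD effect at both visits, the two t tests would disagree in about 14-22% of trials at 352 evaluable, and in 16-25% at 315.

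**What to change.** 1. Make the outcome-measures section, Statistical analyses, Sample size and Table 2 agree on one primary measure. FES is the one the trial is sized on. Primary Hypothesis 2 can keep its list if it points to that measure as the deciding one.
2. Name one FES score (the protocol describes family, services and community levels) and one primary visit, tested at two-sided .05. Twelve months fits the trial's stated time frame, but the choice is the sponsor's. Record it before any data by arm are analysed.
3. Make the competence scale and the other visit secondary, or test them in a stated fixed order.
4. Estimate the early-versus-late difference by the treatment-by-visit contrast, with its confidence interval, from the mixed model already planned.
5. Reword the duration sentence to say that the two comparisons describe the course of the effect under the planned 12 months of coaching.

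The cost is wording only, with no new visits or data. The price is that success can no longer rest on the competence scale or on the non-primary visit alone. Keeping both visits primary at .025 each would instead need about 424 evaluable and 472 recruited, against the stated 352 and 392.
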